### **Blood and other Biological Samples**

*Describe how the sample will be used and indicate, when relevant, the amount of the sample. The IRB wants to know that the sample is sufficient for the purposes of the study, but that sampling is limited to what is minimally necessary.*

*If you've indicated that you intend to store a sample for future use, indicate where the sample will be stored, how long the sample will be stored, and to what purposes the sample will eventually be put. Check the IRB website at*

<https://irb.nyspi.org/investigators/guidance/genetic-research> for specific guidance and additional information about future use of DNA samples.

Blood will be drawn for routine testing of hematology (i.e., number, size and hemoglobin content of red blood cells and number and type of white blood cells) and chemistries (e.g., liver enzymes, electrolytes and renal function) on each of three occasions: initial evaluation, 1 day post psilocybin and three weeks post psilocybin. Approximately 20 cc (= 4 teaspoons) of blood will be obtained on each occasion, or 60 cc = 3 tablespoons total over 4-6 weeks. By contrast, 500 cc is taken on a single occasion when one donates blood.

### Assessment Instruments

List all assessment instruments, indicate who will administer them and their credentials/qualifications. Provide an estimate the duration of each measure. The IRB wants to know that assessments instruments are appropriate measures for the purposes of the study and are no more burdensome than necessary. The IRB will consider the burden of assessment instruments (in terms of time, sensitivity of material, etc.) in the risk/benefit analysis. Please attach copies or otherwise provide all non-standard instruments.

- 5D-ASC – The Five Dimension Altered States of Consciousness Questionnaire measures the acute drug effects in terms of various ways of determining state of consciousness. 10 min.
- BDD-YBOCS – The Yale-Brown Obsessive-Compulsive Scale Modified for BDD is a standard clinician-rated measure of BDD symptom severity. 10 min.
- BDD-REBUS-Q – 2-item questionnaire rating certainty of negative beliefs about self and appearance. 1 min.
- BABS – The Brown Assessment of Beliefs Scale is a clinician-rated scale assessing the intensity of body image belief in BDD. 10 min.
- CGI Clinical Global Impression Scales, Severity and Change – global clinician-rated measures of symptom severity and Change 5 min.
- CSSR – Columbia Suicide Severity Scale 10 min.
- EBI – The Emotional Breakthrough Inventory is an 8-item brief measure intended to index the degree to which an individual experiences his/her emotion during a psilocybin session. It is a visual analogue style scale, typically with units from 0 to 100. 5 min
- QLESQ – The Quality-of-Life Enjoyment and Satisfaction Questionnaire is a self-rated measure. 5 min.
- HAM-D-17 – The 17-item Hamilton Rating Scale for Depression measures the degree of symptom severity in depressed patients.
- Liebowitz Social Anxiety Scale – 24 item scale assessing fear and avoidance of social anxiety 5 min
- MRI Metal Screening Questionnaire - self-rated 5 min.
- MINI - the Mini International Neuropsychiatric Interview, Version 7.0.2, is a standardized, semi-structured interview that produces DSM-5 diagnoses. It is similar to the SCID. 30 min
- PANAS - Positive and Negative Affect Schedule measures the acute emotional drug effects. 5 min

- PhenX Toolkit Hand Dominance Measure – self rated form 5 min.
- Psychological Insight Scale – 7 question assess changes in insight on a visual analogue scale. 5 min
- Qualitative Interview
- SDS – The Sheehan Disability Scale is a patient-reported outcome measure used to assess functional impairment and associated disability. 5 min.
- Somatomap 2D (Ralph-Nearman et al. 2019) – A HIPAA-compliant web-based self-assessment tool for measuring body image perception. It displays an androgynous manikin; the user is asked to imagine it as their own body and draw directly upon it to outline an area of bodily concern. They then provide emotion ratings for each area of concern. Somatomap was built on Chorus, a HIPAA (Health Insurance Portability and Accountability Act)-compliant visual development platform. Chorus is a hosted service provided through the University of California Los Angeles (Areivan et al., 2018). 15 min
- Sleep Questionnaire – 2 items assessing sleep quantity and quality.
- Dysmorphic Concerns Questionnaire (Oosthuizen et al., 1998) – A 7-item self-rated scale assessing dysmorphic beliefs.

**Sections to be completed for studies using IND/IDE Drugs and Devices.**

*Prior to the submission of any study involving a faculty held IND or IDE being approved by the IRB, the IND/IDE holder is required to submit a [form](#) signed by the IND/IDE holder and PI.*

Which are applicable to your study:  Drug  Device  Radiolabeled drug/compound

**Off Label and Investigational Use of Drugs**

Enter the information for all drugs to be used in this study:

Name of the drug	
Manufacturer and other Information	
Approval Status (select one)	 IND application is pending  IND is approved  No IND is required
IND #	
Who holds the IND (i.e., IND Sponsor). If other than PI/CU Investigator, type name of holder.	

## Protocol Summary Form

Which applies:	FDA has determined the IND is not required (provide correspondence)  FDA conditions are met (see “Rules”) – Explain
----------------	---

### Off Label and Investigational Use of Devices

Enter the information for all devices to be used in this study:

Name of the device	
Manufacturer and other Information	
Approval Status (select one)	IDE application is pending  IDE is approved  No IDE is required
IDE #	
Who holds the IDE (i.e., IDE Sponsor). If other than PI/CU Investigator, type name of holder.	
Is the device marketed?	
Which applies:	FDA has determined that IDE is not required  FDA conditions are met (see “Rules”) – Explain  Device is “Non-significant risk” – Explain

### Off Label and Investigational Use of Radiolabeled Drugs / Compounds

Enter the information for all radiolabeled drug/compounds to be used in this study:

Name of the radiolabeled drug/compound	N/A
Manufacturer and other Information	N/A

## Protocol Summary Form

Approval Status (select one)	IND application is pending  IND is approved  RDRC approval is pending  RDRC is approved  No FDA/RDRC approval is required - Explain
IND #	N/A
Who holds the IND (i.e., IND Sponsor ). If other than PI/CU Investigator, type name of holder.	N/A

### Research Related Delay to Treatment

*Research involving participants who are in need of treatment invariably involves delay to care, and this delay is associated with risk. Scheduling of procedures must be carefully organized to minimize delay. Other delay must involve only that minimally necessary to accomplish the aims of the research while respecting subject well-being and safety. Describe the delay, by virtue of research participation in this study, before a participant can receive treatment of known efficacy or standard care routinely offered in the community.*

Participants in the study will need to be free of SSRI medication for at least 2 weeks prior to psilocybin administration and for 3 weeks thereafter, so total delay to an established treatment will be 5 weeks. Patients who for clinical reasons need treatment intervention sooner will be offered established treatment. If patients need to restart SSRI's prior to the psilocybin session, they will be excluded. If they restart after the session, the reason will be documented, and the patient will be followed until the end of study visit provided that informed consent is maintained.

### Clinical Treatment Alternatives

*Describe what other treatment or assessment options are available to subjects who do not participate in research.*

There are no FDA-approved medications for BDD, but SSRIs and specialized BDD-specific CBT have been shown to be efficacious in controlled trials.

## Risks/Discomforts/Inconveniences

*"Risk" is a broad term used to convey the potential for harm, burden, and inconvenience related to research participation. Use this section to provide a comprehensive description of foreseeable physical, psychological, social, interpersonal, and economic risks introduced by the research. Include the source of the information. Consider both the probability and magnitude of harm and its impact. Describe the foreseeable harms associated with the research (untoward effects of a medication) and those related to delay to individualized treatment. Include data from the literature, and local data, if available, on risk rates and subject experiences with research procedures. Describe procedures in place to minimize risk. In general, please create a numbered list of risks/categories of risk, and in general put the list in the order of significance or level of risk, the most significant risks should be listed first.*

1. BDD might not remit or may worsen
2. Psilocybin has not been extensively studied, so both short and especially long-term consequences of its use may not be known at present
3. Known psychological effects of psilocybin include:
  - a. Euphoric mood
  - b. Dissociative experience (i.e., feeling outside one's body or unreal, a distorted sense of time)
  - c. Hallucinations (**which may persist for weeks after dosing**)
  - d. Psychotic experience such as paranoia
  - e. Difficulty with cognition (e.g., trouble adding or solving puzzles)
  - f. Disturbance in attention
  - g. Mood alteration
  - h. Inappropriate affect (e.g., crying when one is not sad or laughing when nothing odd occurred)
4. Known medical effects of psilocybin include:
  - a. clumsiness
  - b. feeling weak
  - c. headache
  - d. hyperreflexia (e.g., the lower leg reacts too strongly when the knee tendon is tapped)
  - e. hyporeflexia (e.g., the lower leg under-reacts when the knee tendon is tapped)
  - f. increased blood pressure
  - g. increased pupil size
  - h. rapid heart beat
  - i. tremor
  - j. vomiting
5. Discomfort of needle sticks and ECG
6. Time commitment to completing forms, and attending evaluation, treatment and follow-up sessions
7. Harm to an unborn or newborn child
8. MRI

Describe procedures for minimizing risks:

1. BDD might not remit - standard medication treatment, such as with an SSRI will be instituted and patient will be referred for CBT or other therapy as clinically indicated.
2. Psilocybin has not been systematically studied, so both short and especially long-term consequences of its use may not be known at present - while unknown risks cannot be minimized, we will minimize the likelihood of such risks occurring unnoticed during the study period by asking re AE's at every post-psilocybin visit and encouraging patients to call between visits should any untoward events occur, whether they think they may be related or not.
3. Known psychologic effects of psilocybin include:
  - a. Euphoric mood - the risk of feeling too good is it can result in rash behavior, as in mania. We anticipate that if euphoria occurs, it will happen on the psilocybin day when the therapist and others are present to monitor and talk the patient down from an overly euphoric mood. As overly euphoric mood is a characteristic of bipolar illness, so to minimize risk the study excludes patients with known bipolar disorder.
  - b. Dissociative experience (i.e., feeling outside one's body or unreal, a distorted sense of time) – We anticipate that if the patient has a dissociative experience, it will occur on the psilocybin day when the therapist will be present to "talk them down" and other clinicians will also be readily available.
  - c. Hallucinations - as with b)
  - d. Psychotic experience such as paranoia - as with b); our anticipation is psychotic experiences will spontaneously remit within hours of the subject receiving psilocybin. If not, the on-call psychiatrist can determine whether to give an antipsychotic medication.
  - e. Difficulty with cognition (e.g., trouble adding or solving puzzles) - again, this will occur on the psilocybin day and will be minimized by therapist support, and it is anticipated to dissipate by the time the patient goes home, or at least by the next day.
  - f. Disturbance in attention - this is also anticipated to mainly occur on the day the patient receives psilocybin, but its impact on functioning will be monitored out to Week 12 using the SDS.
  - g. Mood alteration – mood will be monitored using the HAM-D-17 and the PANAS
  - h. Impaired Psychomotor skills - this will be monitored by clinical observation and is expected to resolve during the treatment day.
  - i. Inappropriate affect (e.g., crying when one is not sad or laughing when nothing odd occurred) – this will be monitored by clinical observation and the PANAS and dealt with as part of the therapist's interaction with the patient.
4. Known medical effects of psilocybin:
  - a. Clumsiness - a staff member will remain with patient at all times ready to prevent falls as needed (e.g., traveling to and from the bathroom)
  - b. Feeling weak - ditto
  - c. Headache - standard headache remedies (i.e., NSAID's)

- 
- d. Hyperreflexia - reassurance and waiting
  - e. Hyporeflexia – reassurance and waiting
  - f. Elevated blood pressure - watchful waiting as to date, the blood pressure has not been documented to get to dangerous levels (i.e., systolic pressure may get to 160 mm Hg); as blood pressure rises typically last 1-3 hours, a short-acting blood pressure lowering medication such as nifedipine could be considered
  - g. Increased pupil size - keep in darkened room (this is the standard lighting in psilocybin rooms)
  - h. Rapid heartbeat - watchful waiting as to date, fast heart rate has lasted 1-3 hours; propranolol could be used but to my knowledge no "rescue" med has been required to date.
  - i. Tremor - this typically lasts 1-3 hours so should not require anything besides reassurance; if severe enough, do not allow hot liquids
  - j. Vomiting - this is unusual and time limited; probably too short-lived for anti-emetic medication to help; could try ginger ale or ginger tea
5. Discomfort of repeated needle sticks and other procedures: experienced, trained phlebotomists will obtain blood
  6. Time commitment to completing forms, and attending evaluation, treatment, and follow-up sessions - we will do everything we can to limit time spent; e.g., if patients must wait for their doctor, they will be instructed to complete their self-report forms
  7. Psilocybin is not considered safe during pregnancy or breast-feeding, because such safety testing has not been done. Therefore, potential participants will be excluded if pregnant, breast feeding or planning to become pregnant during the next 3 months. A pregnancy test will be done at screening. Pregnancy tests will be repeated at least twice during the study (on the day prior to taking psilocybin, and on the day taking psilocybin). Participants will be cautioned that even if a pregnancy test is negative, they could still be pregnant, because these tests cannot detect very early pregnancies (that is, within the first few days). Participants will be excluded if they do not agree use an effective form of birth control before and throughout study participation. Methods of birth control considered to be effective include double barrier methods (condom plus spermicide, or diaphragm plus spermicide), birth control pills, birth control shots and intrauterine devices. Men who are sexually active will also be excluded if they do not agree to using adequate contraception. Female partners of men participating in this study should use one of the acceptable methods of contraception (contraception pills, intrauterine device, bilateral tubal occlusion).
  8. To minimize the risk of MRI we will observe United States Food and Drug Administration (FDA) guidelines for magnet strength and exposure to radio waves. We will exclude people with magnetic metal in their body through careful review and checklist. Participants will be specifically warned about risks of a pacemaker or metal objects inside the body, as well as the need to remove all metal from their clothing and all metal objects from their pockets. Also, although there are no known risks to pregnancy, we will not scan someone who is pregnant, and women in childbearing years will take a pregnancy test just before each MRI scan.

In addition, and not specific to any one of the above, a physician will always be available should the therapist become uncomfortable, whether with physical reactions (such as elevated blood pressure) or behavior (e.g., belligerence) or reported symptoms (reports of psychotic symptoms or suicidality). The therapist's training will be to err on the side of calling the physician unnecessarily rather than allowing the patient's condition to worsen further. While our read of others' experiences with similar doses of psilocybin is situations requiring medical interventions are highly unlikely, we recognize it is important to be prepared for such an eventuality. I have not seen articles documenting the need for rescue medication so can only make the generic suggestion that for difficult psychiatric symptoms, one might first consider a short acting benzodiazepine, such as lorazepam, and then an antipsychotic medication, such as quetiapine. Medical symptoms would be counteracted using appropriate medications, e.g., nifedipine for hypertension. As the half-life of psilocybin and its first metabolite are a few hours it is not surprising that the adverse effects of psilocybin typically last 1-3 hours, so it is likely that should rescue medication be needed it would only require short acting drugs; adverse events that continue into the next day are reported as having been mild (e.g., Hasler et al., 1997) while the only reported late appearing (i.e., not present acutely following psilocybin dose) adverse event is mild-moderate headache lasting < 24 hours.

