## Protocol Summary Form

9. Use of: investigational medication within past 3 months; depot antipsychotic within past 6 months; serotonergic medication within past 2 weeks (6 weeks for fluoxetine). The ADC will not take subjects off medication for the purpose of entering this study.
	
Psychiatric and Medical History

10. Current cognitive-behavioral therapy (CBT) specific for BDD
	
Psychiatric History

11. History of seizure disorder, other than febrile seizure in childhood
	
Medical History

12. Presence of significant or unstable medical illness
	
Medical History, vital signs, EKG, blood and urine tests, physical examination

13. Females who are pregnant, breastfeeding, or sexually active and not willing to use adequate contraception
	
Medical History, urine pregnancy test

14. Presence of any other conditions that would preclude safe administration of psilocybin based on clinical judgement of the PI and/or therapist. This includes but is not limited to any behaviors suggesting the participant will be unable to establish therapeutic alliance with the therapist
	
Psychiatric Assessment

15. Enrollment in any investigational drug or device study in past 30 days
	
Psychiatric History

16. Dissociative Disorder
	
Psychiatric Assessment

Describe whether and how subjects will be provided with additional pertinent information after participation.  
N/A

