**3. Visit 3 (Psilocybin Day, Day 0).** The next day, a study psychiatrist again assesses eligibility; those eligible and agreeable receive their dose of psilocybin (25 mg) and spend the next eight hours (longer if needed) with the two therapists; when deemed appropriate, the patient is accompanied home either by a person of their choosing or a staff member. The patient will be reminded that they should not drive or drink alcohol at least until after the end of Visit 4 (next day). Vital signs are taken prior to their dose of psilocybin and prior to leaving the clinic and a study psychiatrist evaluates prior to their departure for whether their condition requires them not to leave. In the latter case, they will either remain in the Biological Studies Unit (BSU) until

cleared by a study psychiatrist or admitted to 5-South inpatient service if they require additional observation overnight.

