### Hospitalization if needed

- Given prior experience with psilocybin treatment, the need for inpatient hospitalization appears unlikely
- In the event that patients require hospitalization they may be admitted to NYSPI 5-South unit.
- Prior to psilocybin dosing [name] will be contacted (email or text [contact]) to ascertain whether backup 5S inpatient bed at NYSPI will be available. In event of lack of availability for such a bed on 5S after it has been offered (e.g., unanticipated issue on inpatient unit) the NYPH. Emergency Room will serve as backup.

**4. Visit 4 (Post-Psilocybin Day 1).** The patient returns to the anxiety clinic and reports any experiences since leaving the clinic as well as having blood, urine, and EKG tests. MRI eligible patients will have another resting state fMRI session, The inverted face task will be repeated.

**5. Visits 5-8 (Post-Psilocybin Weeks 1-3 and 12).** The patient returns 1, 2, 3 and 12 one week later for standard evaluation of psychiatric symptoms, functioning and AE's. These visits may be conducted by phone or secure video.

**6. Telephone visits (Weeks 6 & 9).** The patient is contacted by telephone 6- and 9-weeks post-psilocybin for standard evaluation of psychiatric symptoms and AE's.

**7. Early Withdrawal Visit.** Should the patient or study doctor decide to end the study visits prior to Week 12, if the patient agrees, all Visit 10 (Week 12) ratings including Independent Evaluation will be made.

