## Protocol Summary Form

BDD-REBUS-Q	X		X	X	X	X	X	X	X	X	X	X
Brown Assessment of Beliefs Scale	X		X	X	X	X	X	X	X	X	X	X
Physical Examination	X											
ECG	X				X							
Urinalysis	X		X		X							
Urine for drug/alcohol screening	X		X									
Urine for pregnancy testing*	X		X		X							
Blood for routine laboratory assays	X				X			X				
Vital signs	X		X	X	X							
Height and Weight	X											
PhenX Toolkit Hand Dominance Measure	x											
MRI Metal Screening Questionnaire	x		x		x							
Inclusion & Exclusion Criteria	X		X									
Adverse Events/SAE		X		X	X	X	X	X	X	X	X	X
Resting State fMRI			x		x							
Inverted Face Task			x		x							
Clinical Global Impression - Change					X	X	X	X	X	X	X	X
5Dimension-Altered States of Consciousness				X								
Emotional Breakthrough Inventory					X							
Positive and Negative Affect Schedule			X		X			x	x			
Liebowitz Social Anxiety Scale			x		X				x			X
Psychological Insight Scale					X			X	X			X
Somatomap – 2D Tool			x		x							x
Sheehan Disability Scale			X						x			X
Qualitative Interview				x	x							
Sleep Questionnaire			x		x							
Dysmorphic Concerns Questionnaire			x		x			X	X			x

At any visits in which patient reports clinical worsening, HamD, CSSR, and CGI will be repeated.

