6. Potential pregnancy: Participants who prior to dosing have a positive pregnancy test or report suspecting pregnancy will be removed from the study. Participants who after dosing have a positive pregnancy test will be excluded from the repeat MRI but will be allowed to continue in study assessments of symptoms. They will be offered assistance with obstetrical follow-up

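### The risk section promises a pregnancy test on the dosing day, but the visible schedule marks tests at screening, Day -1 and Day +1 and none at the dosing visit

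*Combined protocol and SAP*

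**What the plan says.** The list of procedures for minimizing risks (under Risks/Discomforts/Inconveniences) treats pregnancy in item 7. It says that safety in pregnancy has not been tested, calls for a pregnancy test at screening, and continues: "Pregnancy tests will be repeated at least twice during the study (on the day prior to taking psilocybin, and on the day taking psilocybin". Item 8 adds a different rule, tied to imaging: women in their childbearing years are tested shortly before each scan.

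The Table - Schedule of Study Procedures has a row labelled "Urine for pregnancy testing", followed by an asterisk whose note is not in the text available for review. The row is marked at Visits 1, 2 and 4.

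Four other places bear on the point:

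- Under Study Procedures, Visit 3 (Day 0), "a study psychiatrist again assesses eligibility; those eligible and agreeable receive their dose of psilocybin (25 mg" is the instruction on eligibility.
- Exclusion 13 covers pregnancy, and its method of ascertainment is "Medical History, urine pregnancy test".
- Under Visit 4 (Day +1), "MRI eligible patients will have another resting state fMRI session".
- Criteria for Early Discontinuation, item 6, has one rule for each side of dosing: "Participants who prior to dosing have a positive pregnancy test or report suspecting pregnancy will be removed from the study", and "Participants who after dosing have a positive pregnancy test will be excluded from the repeat MRI". It names no test days.

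**The concern.** Two operative parts of the same protocol give different days for a safety test. Item 7 puts the last test before exposure on the dosing day; the schedule puts it on the day before. The schedule's other repeat, on Day +1, cannot replace a Day 0 test, because by then the drug has been taken.

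Sites usually run visits from the schedule. If nothing else prompts the test, the participant is dosed on the Day -1 result, and a safeguard offered against a listed risk (harm to an unborn or newborn child, item 7 of the risk list) is left out. What is at stake is adherence to a stated protection. The statistical analysis is not involved.

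**Working it through.** No sample size, power or error rate enters here, so the check is a reading of the schedule against the text.

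**Step 1. Column order.** The header runs: Visit 1 (screening); 1a, 1b, 1c (screening period); 2 (Day -1); 3 (psilocybin); 4 (Day +1); 5 (+7); 6 (+14); 7 (+21); 8 (+42); 9 (+63); 10 (+84).

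**Step 2. The pregnancy row.** Its cells are X, blank, X, blank, X. In header order these are Visit 1, Visit 2 and Visit 4. The cells for the 1a-1c visits and for Visit 3 are blank.

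**Step 3. Is the alignment sound?** Some rows in the second half of the table, such as BDD-REBUS-Q, carry one cell more than the header, so the alignment was tested on rows whose timing the text gives independently.

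| Row | Cells read as | Text elsewhere | Agree? |
|---|---|---|---|
| Resting state fMRI | Visits 2, 4 | Visit 2 and Visit 4 narratives | Yes |
| ECG | Visits 1, 4 | Visit 1 and Visit 4 narratives | Yes |
| Blood | Visits 1, 4, 7 | Blood and other Biological Samples: initial evaluation, one day and three weeks after dosing | Yes |
| Vital signs | Visits 1, 2, 3, 4 | Visit 3 narrative: before the dose and before leaving | Yes, at Visit 3 |

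The surplus cell lies at the right-hand end, and the columns for Visits 1 to 4 line up. A mark can appear at Visit 3 (vital signs has one), so the blank in the pregnancy row is not a loss of that column.

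**Step 4. The sources side by side.**

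| Time point | Item 7 | Item 8 (woman who is scanned) | Schedule |
|---|---|---|---|
| Screening | Test | - | Test |
| Day -1 | Test | Test | Test |
| Day 0, before dose | Test | - | Blank |
| Day +1 | - | Test | Test |

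Item 7 and the schedule agree on screening and Day -1. Day 0 is only in item 7. Day +1 is in the schedule and is explained by item 8. A scanned woman needs 4 tests to satisfy items 7 and 8 together (screening, Day -1, Day 0, Day +1). The schedule marks 3, so one is unmarked: 4 - 3 = 1.

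**Step 5. How many people.** The continuation report gives 8 female and 4 male participants, 8 + 4 = 12. At most 8 are concerned, and fewer if some are not of childbearing potential; the documents do not say how many are.

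**The case against.** The strongest reply is that a blank cell in the visible table does not prove that no test was planned or done. It has four parts.

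1. **The asterisk.** The row points to a note that cannot be read here, and that note could add a test at Visit 3. This stands, and the conclusion is conditional on it.

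2. **The Day 0 eligibility check.** A psychiatrist reassesses eligibility before dosing, and pregnancy is an exclusion ascertained by urine test. The schedule evidently under-lists that visit: its row for inclusion and exclusion criteria is marked only at Visits 1 and 2, although the narrative requires reassessment on Day 0. So the check could include a test. No visible text says that it does, and no urine collection of any kind is marked at Visit 3; the row "Urine for drug/alcohol screening", for example, stops at Visit 2.

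3. **Which text is wrong?** Item 7 asks for at least two repeats after screening, and the schedule gives two. Only the day of the second differs, so the slip could be in item 7. The documents do not settle this. The conflict is there either way, and item 7 is the explicit commitment.

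4. **Little is lost.** A repeat one day after a negative test adds little, item 7 itself concedes that very early pregnancies escape detection, contraception is required, and anyone who suspects pregnancy before dosing is removed. This stands and limits the size of the point.

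A reader might also infer, from the absence of a pregnancy test in the Visit 3 narrative, that none was intended. That inference is not supported: the Visit 2 and Visit 4 narratives name none either, although the schedule marks one at both.

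**Conclusion.** The inconsistency is real and minor. Item 7 commits to a pre-dose test on Day 0, and the visible schedule does not carry it. Unless the asterisk note or the Day 0 eligibility reassessment supplies the test, staff who follow the schedule would leave out a safeguard that the plan promises.

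The size is one unmarked pre-dose test per woman of childbearing potential, at most 8 women. The safety consequence is small, since a Day -1 test is scheduled, and no efficacy or tolerability result changes.

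A reader might go further and conclude that women were dosed without a dosing-day test. The documents do not support that: they show a scheduling mismatch, contain no testing records, and report no serious adverse events. The conclusion rests on the column reading, which four independent rows confirm, and on the unseen note not adding a Visit 3 test. Confidence is moderate for that reason.

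**What to change.** Reconcile the two texts. Mark a pre-dose urine pregnancy test at Visit 3 in the schedule, and keep the Day +1 mark for the pre-MRI rule.

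As all interventions are finished, the step that matters for this trial is a records check: for each woman of childbearing potential (at most 8), see whether a pre-dose test was done on Day 0, and note any omission against item 7 in the safety report.

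The cost now is up to 8 records and one sentence. If the protocol is reused, it is one schedule mark, one urine test at a visit already attended, and a few minutes' wait before dosing.
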